#### 11.1 Adverse Events

AEs will be classified using the MedDRA version 22.0 or higher classification system. The severity of the toxicities will be graded according to the National Cancer Institute Common Terminology Criteria for Adverse Events (NCI CTCAE) v5.0 or later. Treatment-emergent adverse events (TEAEs) are defined as events with an onset date on or after the date of first dose of study medication until the date of the last oral study medication plus 28 days or date of last IV dose plus 5 months (ie, 152 days), whichever is the latest date. Also, AEs will be considered treatment-emergent if all or part of the date of onset of the adverse event is missing and it cannot be determined if the AE meets the definition for treatment-emergent.

The number and percentage of patients who experienced TEAEs for each SOC and PT will be presented. Multiple instances of the TEAE in each SOC and multiple occurrences of the same PT are counted only once per patient. The number and percentage of patients with at least one TEAE will also be summarized.

Separate tables will be presented as follows:

- All TEAEs;
- TEAEs by CTCAE grade;
- Grade 3 or greater TEAEs;
- Treatment-related TEAEs, for oral treatment and IV treatment separately, and also both;
- Serious TEAEs;
- TEAEs with an outcome of death;
- TEAEs leading to discontinuation of study medication for oral treatment and IV treatment separately, and also both;
- TEAEs resulting in reduction oral study medication;
- TEAEs resulting in interruption of oral treatment and IV treatment separately, and also both;
- TEAEs resulting in reduction or interruption of oral treatment;
- Time to the first TEAE that results in a reduction of oral treatment;
- Time to the first TEAE that results in an interruption of oral treatment or IV treatment separately, and also both;
- Time to the first TEAE that results in discontinuation of oral treatment or IV treatment separately, and also both.

The incidence of TEAEs will be summarized by relationship to either oral or IV study drug according to the following categories: "treatment-related," or "not treatment-related". If a patient experiences multiple occurrences of the same AE with different relationship categories, the patient will be counted once, as a relationship category of treatment related.

If a patient experiences multiple occurrences of the same AE with different toxicity grades, the patient will be counted once for the maximum (most severe) toxicity grade. AEs with a missing toxicity grade will be presented in the summary table with a toxicity grade of "Missing." For each toxicity grade, the number and percentage of patients with at least one TEAE of the given maximum grade will be summarized.

The time to the first TEAE and first treatment-related TEAE that results in a dose reduction, delay, interruption, or discontinuation for oral study drug and for IV study drug is defined as 1+ the number of days from the first dose of study drug to the start of the first adverse event. The cumulative incidence is presented in a 1-KM graph for just the patients with an event and the median time to onset will be calculated together with the 95% CI.

Non-TEAEs (pre-treatment and post-treatment) will be presented in the by-patient data listings for the safety population.

MedDRA PTs will be combined for the following similar terms:

- Anaemia or Haemoglobin decreased;
- Asthenia or Fatigue;

Confidential 41 of 52

- ALT or AST increased;
- Neutropenia or Neutrophil count decreased;
- Thrombocytopenia or Platelet count decreased.

In addition, the analysis of combined terms for anemia is explored as a time to first event analysis as described above. Transfusions (blood or plasma) and concomitant medications/growth factor support are provided in patient listings. The number of transfusions and the time to first transfusion will also be summarized.

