- u = First dose of IV study drug occurs C2D1. Study treatment continues on Day 1 every 28-day cycle until 24 months after initiation of oral/IV combination study treatment, disease progression, or unacceptable toxicity, whichever happens first.

Table 5. Schedule of Assessments for All Patients (cont.)

- V = AEs, SAEs, and AESIs that occur after first administration of study drug through to 28 days after last dose of oral or IV study drug, whichever occurs later, and AEs/SAEs assessed as related to IV drug that occur up to 5 months after the last IV dose of study drug will be recorded. In addition, AEs that were related to a screening procedure will also be recorded. Section 8 includes the details of reporting AEs, SAEs, and AESIs. Ongoing SAEs, AESIs, or treatment-related Grade 3/4 AEs will be followed to resolution or stabilization. After the 28-day (oral) or 5-month (IV) windows, only SAEs considered as potentially study-drug related (including serious reports of pneumonitis or similar events, ie, interstitial lung disease, pulmonary fibrosis, acute interstitial pneumonitis, alveolitis necrotizing, alveolitis, hypersensitivity pneumonitis, and organizing pneumonia, if considered to be related to study drug), and AESIs of myelodysplastic syndrome (MDS) and acute myeloid leukemia (AML) regardless of causality, will be recorded. If a patient discontinues from treatment and begins a subsequent anticancer therapy, the sponsor will terminate collection of SAEs, with the exception of the AESIs of MDS and AML.
- w = An optional tumor biopsy may be collected from patients at time of disease progression/randomized treatment discontinuation. Additional consent is required. Refer to the central Laboratory Manual for detailed sample collection and handling instructions.
- x = All patients discontinued from treatment, regardless of reason, should be followed for subsequent treatments, secondary malignancy, and survival every 12 weeks (± 14 days) after SFU1 (28-days after the last dose of study drug) until death, loss to follow-up, withdrawal of consent from study, or closure of the study. Follow-up can be performed via the telephone. Diagnosis of any secondary malignancy requires appropriate documentation (ie, laboratory and/or pathology reports) and should be reported as specified in Section 8.7.

Table 6. Pharmacokinetic and Immunogenicity Sample Collections

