8.6 Pregnancy or Drug Exposure During Pregnancy

Pregnancy is an exclusion criterion. In addition, due to inclusion criteria #4, requiring at least a bilateral salpingo-oophorectomy and partial omentectomy, women of child-bearing potential will not be randomized in this study.

All study participants must avoid pregnancy achieved through assisted reproductive technology, for the duration of study treatment and for a minimum of 6 months following the last dose of study drug (oral or IV, whichever is later).

8.7 Recording of Adverse Events, Serious Adverse Events, and Adverse Events of Special Interest

Events that occur after signing of informed consent but prior to initiation of study drug, unless due to a protocol-mandated procedure, should be recorded on the Medical History eCRF; however, events are to be reported as SAEs if serious and related to a protocol-mandated procedure during this time. Any AE (serious or non-serious) that occurs after first dose of study drug through 28 days after receiving the last dose of oral or IV study drug, whichever occurs later, will be recorded on the AE eCRF. Additionally, only AEs that are related to IV drug that occur between 28 days and 5 months after the last dose of IV drug will be recorded on the AE eCRF.

After the 28-day reporting window following discontinuation of randomized treatment, only SAEs assessed as potentially related to study drug should be reported.

After the 28-day or 5-month reporting window after discontinuation of randomized treatment, AESIs of MDS and AML, irrespective of causality, should be reported.

• AESIs of pneumonitis or similar events should only be reported up to, but not beyond, the SFU1 (28-days after the last dose of rucaparib). After this period, only events considered serious and related to study drug should be reported as SAEs (including serious reports of pneumonitis or similar events, ie, interstitial lung disease, pulmonary fibrosis, acute interstitial pneumonitis, alveolitis necrotizing, alveolitis, hypersensitivity pneumonitis, and organizing pneumonia), if considered to be related to study drug.

Information on the follow-up of AEs, SAEs, and AESIs is provided in Section 8.8.

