- Disease status (no residual disease vs residual disease); and
- Timing of surgery (primary surgery vs interval debulking).

Randomization to study treatment must occur within 8 weeks following a patient's first day of the last cycle of chemotherapy.

During the Double-blind Treatment Phase (continuous 28-day treatment cycles), the double blinded oral study treatment will be administered on Day 1 of Cycle 1 and continue BID throughout the cycle as monotherapy. IV study drug administration will begin on Day 1 of Cycle 2 during the Double-blind Treatment Phase. Patients will have clinic visits on Day 1 and Day 15 of Cycles 1 and 2, and on Day 1 of every cycle thereafter. Study treatments will continue until 24 months after planned initiation of oral/ IV combination study treatment (C2D1), disease progression, unacceptable toxicity, or withdrawal of participant consent, whichever happens first.

During the Treatment Phase patients will be monitored for safety and efficacy. Assessments will include AEs, physical examination, vital signs and weight measurement, central laboratory hematology, serum chemistry, and CA-125 measurement, concomitant medications, therapies, and procedures, ECOG performance status, disease status assessment, ctDNA analysis, study drug administration and accountability, and PRO. ECGs and urinalysis will be performed as clinically indicated. Blood samples will also be collected to determine whether any mutation identified is of germline or somatic origin.

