#### 11.2 Immune-Mediated Adverse Events

Adverse events that meet the definition of Immune-Mediated AEs will be summarized similarly as described in Section 11.1.

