If a patient experiences multiple occurrences of the same AE with different toxicity grades, the patient will be counted once for the maximum (most severe) toxicity grade. AEs with a missing toxicity grade will be presented in the summary table with a toxicity grade of "Missing." For each toxicity grade, the number and percentage of patients with at least 1 TEAE of the given maximum grade will be summarized.

The time to the first TEAE of Anaemia or Haemoglobin decreased, and first TEAE leading to a dose reduction, interruption, and/or discontinuation of oral study drug is defined as 1+ the number of days from the first dose of study drug to the start of the first AE. The cumulative incidence is presented in a 1-KM graph for only the patients with an event and the median time to onset will be calculated together with the 95% CI.

Non-TEAEs (pre-treatment and post-treatment) will be presented in the by-patient data listings for the Safety Population.

MedDRA PTs will be combined for the following similar terms:

- Anaemia or Haemoglobin decreased;
- Asthenia or Fatigue;
- ALT or AST increased;
- Neutropenia or Neutrophil Count decreased;
- Thrombocytopenia or Platelet count decreased.

In addition to the cumulative incidence tables of AEs, time adjusted AE summaries for the oral treatment study duration will be created. The time adjusted analyses (ie, 100 patient-treated years) of AEs are defined as the number of total events of a certain AE divided by the patient-years. The patient-years is the total sum of all the years the patients in each treatment arm are treated (ie, from the start of first oral dose to date of last oral dose +1 day). The time adjusted analyses will be summarized for the following:

- 100 patient-treated years for all TEAEs;
- 100 patient-treated years for Grade 3 or greater TEAEs; and
- 100 patient-treated years for serious TEAEs.

In addition, the analysis of combined terms for anemia is explored as a time to first event analysis as described above. Transfusions (blood or plasma) and concomitant medications / growth factor support are provided in patient listings. The number of transfusions is also summarized.

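### ATHENA-COMBO gives all, Grade 3+, serious and immune-mediated TEAEs only as numbers and percentages of patients; a rate per time at risk, of the kind ATHENA-MONO plans for the first three, would be a cheap supplement

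*SAP*

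**What the plan says.** COMBO SAP 11.1: "The number and percentage of patients who experienced TEAEs for each SOC and PT will be presented". A preferred term counts once per patient. All, Grade 3+ and serious TEAEs each get a table. For immune-mediated events, 11.2 says: "Adverse events that meet the definition of Immune-Mediated AEs will be summarized similarly as described in Section 11.1".

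The COMBO SAP is not silent on time. Section 7.1 summarises oral and IV treatment duration, dose intensity and IV cycles. Section 11.1 plans time-to-first displays for TEAEs that lead to dose modification or discontinuation, for combined anemia terms and for transfusion. Of the graph it says: "The cumulative incidence is presented in a 1-KM graph for just the patients with an event". None of this is a rate over all time at risk.

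Under COMBO SAP 2.2, treatment ends at 24 months after planned C2D1, "disease progression, unacceptable toxicity, or withdrawal of participant consent, whichever happens first". On the IV drug: "IV study drug administration will begin on Day 1 of Cycle 2 during the Double-blind Treatment Phase".

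MONO SAP 11.1 adds rates per 100 patient-treated years for all, Grade 3+ and serious TEAEs. These "are defined as the number of total events of a certain AE divided by the patient-years", with years running from first to last oral dose.

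**The concern.** A crude percentage depends on how long patients are exposed as well as on how toxic the treatment is. Treatment stops for progression and for toxicity, so time at risk can differ by arm. Section 11 shows the four arms side by side, and safety is a secondary objective. A difference in percentages could then be read as a difference in toxicity when part of it is exposure, or a real difference could be masked. The duration table is not linked to the AE counts, and a curve limited to patients with an event cannot correct for unequal time at risk. The sister SAP adds time-adjusted summaries for three of the four categories; COMBO omits them without giving a reason.

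**Working it through.** The plan states no figure to reproduce here, so this is an illustration of size.

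**Inputs from the documents**
- Median PFS: A 28 and B 20 months (COMBO SAP 2.4); D 12 months (MONO SAP 2.3.2).
- Treatment cap: 24 months after C2D1, taken as month 25 from first dose.

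**Assumptions (the documents give no values)**
- Exponential progression; treatment stops at progression or the cap. Treatment beyond progression, which the SAP allows, is not modelled.
- One first-event rate r per month, equal in all arms, varied from 0.002 to 0.2.
- Extra stopping d per month in Arm A, zero unless stated.

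**Step 1: mean exposure.** h = ln2/median + d; mean = (1 − exp(−25h))/h. Results: A 18.6, B 16.7, D 13.2 months. Ratios: A/B 1.11, A/D 1.41.

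**Step 2: crude incidence** with events counted for w = 28/30.4375 = 0.92 months after the last dose:

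1 − exp(−wr) × [h/(h+r) × (1 − exp(−25(h+r))) + exp(−25(h+r))]

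| r per month | A % | B % | D % | A−B | A−D |
|---|---|---|---|---|---|
| 0.002 | 3.8 | 3.5 | 2.8 | 0.4 | 1.0 |
| 0.02 | 31.4 | 28.6 | 23.5 | 2.8 | 7.9 |
| 0.05 | 58.5 | 54.1 | 45.8 | 4.4 | 12.7 |
| 0.2 | 90.6 | 87.5 | 81.3 | 3.1 | 9.3 |

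Gaps are taken before rounding. The A−B gap peaks at 4.7 points (r near 0.074) and A−D at 13.6 (r near 0.077). For scale, the standard error of a 400 versus 400 difference at r = 0.02 is √[(0.314×0.686 + 0.286×0.714)/400] = 3.2 points.

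**Step 3: direction.** The A−B gap vanishes at d = ln2/20 − ln2/28 = 0.0099 per month. At d = 0.02 it is −2.4 points for r = 0.02, and −4.2 at its most negative.

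**Step 4: immune-mediated events.** Same formula, counted from C2D1 with a 24-month cap, r = 0.02.
- To 28 days after the last IV dose (w = 0.92): 30.7, 28.1 and 23.2%; A−B 2.6, A−D 7.5.
- To 152 days (w = 152/30.4375 = 4.99): 36.1, 33.7 and 29.2%; A−B 2.4, A−D about 7; peaks 3.5 and 10.1.

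**Step 5: the rate removes the gap only if the windows match.** With events and person-time both ending at first event or 28 days after the last dose, person-time per patient is incidence/r. The rate is then 1200 × 0.02 = 24.0 per 100 patient-years in every arm. If events stop at 28 days but person-time runs to 5 months, person-time gains (1 − incidence) × (5 − 0.92), and the rates become 20.4, 19.9 and 19.0.

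**Step 6: where the rate misleads.** Suppose 30% of each arm has an event at month 1 (assumed). The rate is 1200×0.3/[0.3×1 + 0.7×(mean exposure + 0.92)] = 25.7 (A), 28.5 (B) and 35.3 (D). A looks 10% lower than B and 27% lower than D although the percentages are equal.

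**Step 7: near-universal categories.** At r = 1 per month the A−B gap is only 0.4 points. About (1 − exp(−0.92))/0.987 = 61% of Arm B first events then fall in the oral-only Cycle 1.

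**The case against.** The strongest case against is that this is a preference for an extra table. Protocol 9.7.1 specifies numbers and percentages, so COMBO contradicts nothing. MONO had more need of rates: it compared active with placebo, with patients still on treatment at cut-off. COMBO SAP 7.1 says every patient will be off treatment by cut-off, and both main arms take rucaparib under one cap. The modelled A versus B effect at r = 0.02 is below its standard error, rests on assumed event rates and needs the planned PFS gain to be real. A constant rate brings its own distortion: Protocol 5.6.1.2 places rucaparib's ALT/AST rises at Cycle 1 Day 15, the early-onset pattern in which the longer-exposed arm looks safer.

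Most of this stands, and it sets the severity. It does not remove the point. Being off treatment at cut-off does not equalise exposure, A versus D is more affected, and a reader cannot correct mentally for a bias of unknown sign.

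Three stronger readings are tempting, and the documents do not support them.

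- **That Arm A's percentages will be inflated.** Step 3 shows that the sign depends on how much extra stopping the combination causes.
- **That general AEs are recorded only to 28 days, so the SAP's 152-day window is simply wrong.** Protocol 8.7 does say that "only AEs that are related to IV drug that occur between 28 days and 5 months after the last dose of IV drug" go on the AE form, and Table 5 footnote v agrees. But 8.7 also requires all SAEs and AESIs, related or not, to 5 months after IV drug; 8.10 repeats this, and 7.5.4.1 extends monitoring of all AEs that far. The protocol is inconsistent after 28 days.
- **That no time-based display reaches immune-mediated events.** The reference in 11.2 back to 11.1 may carry over the dose-modification time-to-first displays, but it still adds no rate.

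**Conclusion.** The point holds as a low-severity improvement, not as an error. The COMBO SAP has no AE rate per time at risk for these four categories, while treatment length depends on efficacy and tolerability. Under the planning medians, equal assumed event rates and no extra stopping, the spurious gap is at most 4.7 points for A versus B and 13.6 for A versus D. The A versus B sign is uncertain. Safety is descriptive, so only the reading of the tables changes. The gain is clearest for Grade 3+, serious and immune-mediated events. For all TEAEs the rate adds little if nearly every patient has an event.

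**What to change.** Keep the percentages. Beside them, give by arm the number of patients with a first event per 100 patient-years, with events and person-time on the same window.

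1. **Grade 3+ and serious TEAEs, and all TEAEs for consistency with MONO.** Count from first dose to the earliest of first event, 28 days after the last oral or IV dose (whichever is later), start of subsequent anticancer therapy, or death. The 28-day limit is the longest window on which the protocol sections agree. Later serious TEAEs stay in the percentages. The clock stops at new therapy because, once a patient "begins a subsequent anticancer therapy, the sponsor will terminate collection of SAEs, with the exception of the AESIs of MDS and AML". Note beside the all-TEAE rate that a near-universal category saturates and is dominated by oral-only Cycle 1 events.
2. **Immune-mediated AEs.** Count from first IV dose to the earliest of first event, 28 days after the last IV dose, subsequent therapy, or death. Patients with no IV dose are left out. Add a version to last IV dose + 152 days restricted to IV-related immune-mediated AEs, which are recorded that long.
3. **Caveat.** State that constant-rate summaries can make the longer-exposed arm look safer for early-onset events, so the rates supplement the percentages and do not replace them.

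The MONO definition should not be copied unchanged: it divides total events by time to the last oral dose, while its TEAE window runs 28 days longer.

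The cost is SAP wording and a few tables from AE, dosing and subsequent-therapy dates already collected. The downside is the early-onset distortion shown in Step 6.

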## 3 GENERAL ANALYSIS CONVENTIONS

Efficacy analyses will be analyzed in the ITT Population as described in Section 10 below.

All safety analyses will be based on the Safety Population, which consists of all patients who received at least 1 dose of protocol-specified treatment of oral study drug and/or IV study drug. Further, for safety analyses, patients randomized to either arm containing IV Nivolumab (ie, Arm A or Arm C) who never receive Nivolumab, will be analyzed in the analogous arm containing IV Placebo (ie, Arm B or Arm D, respectively).

Quantitative variables will typically be summarized using frequencies and percentages for appropriate categorizations and may also be summarized using descriptive statistics. For variables summarized with descriptive statistics, the following will be presented: N, mean, standard deviation, median, minimum, and maximum. Categorical variables will be presented using frequencies and percentages.

The Kaplan-Meier methodology will be used to summarize time-to-event variables. The 50th (median) percentile with the 95% CI will be summarized for each randomized treatment group. The stratified hazard ratio from the Cox proportional hazards model will be used to estimate the HR between the randomized treatment groups. The number of patients with events and the number of censored patients will also be presented.

The primary endpoint of invPFS, secondary endpoint of OS, bicrPFS (if applicable), ORR and exploratory analyses for the ITT population will be analyzed using the stratification factors of HRD classification, disease status, and timing of surgery. If the model does not converge or if there are only patients from a single treatment arm per stratum or if one or more of the strata contain few patients (eg, <5 patients) then the stratification factor of disease status will be omitted first, then timing of surgery, if necessary. Additionally, the Firth correction in the PHREG procedure will be used.

All data will be used to the maximum possible extent but without any imputations for missing data.

Baseline is defined as the last measurement on or prior to the first day of oral study drug administration or randomization date if the patient was never treated.

Results of all statistical analysis will be presented using 95% CIs and two-sided p-values. The significance level for ATHENA-COMBO is set at a one-sided p=0.0125 (two-sided p=0.025).

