## Table 4 Key Parameters used to Calculate Exposure

#### Administration of study therapy: definition of parameters

	Rucaparib	Nivolumab
Dosing schedule per protocol	600 mg BID	480 mg every 4 weeks
Dose	Dose (mg) is defined as Total Dose administered. Dose administered in mg at each dosing date are collected on the eCRF.	Dose (mg) is defined as Total Dose administered. Dose administered in mg at each dosing date are collected on the eCRF.
Relative dose intensity (%)	Time normalized actual dose received /600 mg BID	[Cumulative dose (mg) / ( (Last dose date – first dose date + 28) $\times$ 480/28)] $\times$ 100
Duration of treatment	Last dose date - Start dose date +1	Last dose date - Start dose date +1

Oral and IV study drug exposure will be summarized for all patients in the Safety Population. At the time of the visit cut-off, all patients will have discontinued treatment for protocol-specified reasons or because they reached the treatment cap of 24 months for treatment with the oral/IV combination. The duration will be summarized with summary statistics and by categories (0 to 6 months,  $\geq$  6 to 12 months,  $\geq$  12 to 24 months,  $\geq$  24 months) for each treatment arm.

For oral study drug, the number of patients with at least 1 dose reduction due to a TEAE based on the dosing log will be summarized with frequencies and percentages. Any dose reduction regardless of duration will be summarized. In addition, protocol-specified dose reductions will be broken up by dose level and by reason (ie, AE, non-compliance, or other). That is, the number of patients on each protocol-specified oral dose level will be summarized (ie, 600 mg BID, 500 mg BID, 400 mg BID, 300 mg BID, etc.) in order to assess patients with multiple levels of oral dose reductions. Dose reduction is defined as 3 or more consecutive days at that protocol-specified dose level. The number of patients with at least 1 dose re-escalation will be summarized for each protocol-specified oral dose level from which they escalated.

The number of IV cycles given per treatment arm will also be summarized.

The following parameters will also be summarized for IV study drug:

- Cumulative dose (sum of the doses administered per patient) and infusion duration (stop time start time for each infusion).
- Dose delays: number of patients with at least 1 delay, number of delays per patient, reasons for delays, and length of delays.

Confidential 27 of 52

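### ATHENA-COMBO SAP 11.1 draws the cumulative incidence of dose-modifying adverse events and anaemia only in patients who had the event, so every curve ends at 100% and cannot show risk by arm

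*SAP*

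**What the plan says.** ATHENA-COMBO SAP 11.1 defines a time variable running from first dose to the start of the first qualifying adverse event, plus one day. The qualifying events are the first TEAE and the "first treatment-related TEAE that results in a dose reduction, delay, interruption, or discontinuation for oral study drug and for IV study drug". On presentation it says: "The cumulative incidence is presented in a 1-KM graph for just the patients with an event". A median time to onset with a 95% CI accompanies the graph. For anaemia, "the analysis of combined terms for anemia is explored as a time to first event analysis as described above", which is most naturally read as the same method.

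No censoring rule is given for these curves, and neither a risk set of all treated patients nor a competing event is named.

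Three other provisions bear on the point:

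- Section 11.2 says: "Adverse events that meet the definition of Immune-Mediated AEs will be summarized similarly as described in Section 11.1". It does not say whether the graph is included.
- Events without a full onset date are kept in the tables: "AEs will be considered treatment-emergent if all or part of the date of onset of the adverse event is missing" and their status cannot otherwise be determined. Section 3 says: "All data will be used to the maximum possible extent but without any imputations for missing data". Such events may therefore have no time to plot.
- ATHENA-MONO SAP 11.1 has the same rule: "The cumulative incidence is presented in a 1-KM graph for only the patients with an event".

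**The concern.** A cumulative incidence at time t is the proportion of all treated patients in an arm who have had the event by t. Its denominator must include those who never have it. Restricting the set to patients with the event removes exactly the information that distinguishes a high-risk arm from a low-risk one.

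Section 11 of the COMBO SAP measures safety by incidence and shows it by arm. As specified, a graph described as cumulative incidence would reach 100% in every arm, beside tables giving, say, 15% and 30%. A reader weighing rucaparib plus nivolumab against rucaparib could conclude that the arms do not differ in events that change study drug dosing, when the graph is unable to show whether they do.

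**Working it through.** The documents give no adverse-event risks or onset times and state no figure on this point, so there is nothing to reproduce. The 100% endpoint needs no outside input. The remaining steps use assumed inputs.

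**1. Endpoint.** Let k patients in an arm have the event. All are in the set and none is censored. The Kaplan-Meier estimate after the last onset is the product over i = 1 to k of 1 − 1/(k − i + 1). The last factor is 1 − 1/1 = 0, so 1-KM = 100% for any k ≥ 1. For k = 4: 3/4 × 2/3 × 1/2 × 0 = 0.

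**2. What the curve estimates.** Let p be the arm's risk and F(t) the distribution of onset times among cases. The cumulative incidence is p × F(t). The events-only curve is F(t) alone, so p has dropped out.

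**3. Equal timing.** Assume exponential onset truncated at 25 months (about one oral-only cycle plus 24 months), a median of 2 months in both arms, and risks of 15% (Arm B) and 30% (Arm A). Then F(6 months) = 0.875.

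| At 6 months | Arm B | Arm A | Difference |
|---|---|---|---|
| Cumulative incidence, p × F | 0.15 × 0.875 = 13.1% | 0.30 × 0.875 = 26.3% | +13.1 points |
| Graph as planned, F | 87.5% | 87.5% | 0 |

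**4. Numerical check.** Assumptions: 400 treated patients per arm (the planned size of Arms A and B), the same exponential onset in both arms (mean 4 months), and end of observation in event-free patients exponential with mean 20 months, capped at 25 months.

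| Risk, A vs B | Events-only 1-KM, end | All treated, Aalen-Johansen, end | All treated, 1-KM with censoring, end |
|---|---|---|---|
| 60% vs 30% | 100% vs 100% | 60% vs 30% | 69.8% vs 35.1% |
| 30% vs 10% | 100% vs 100% | 30% vs 10% | 34.8% vs 11.8% |
| 15% vs 5% | 100% vs 100% | 15% vs 5% | 18.3% vs 6.1% |

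**5. Why restoring the full risk set is not enough.** The last column of the table exceeds the true proportions because ordinary 1-KM treats patients who have left observation as if they could still have the event. A closed-form case shows the same. Take an event hazard of 0.01 per month, a competing stop with median 20 months (hazard ln 2/20 = 0.0347) and a cap at 25 months. The proportion with the event is [0.01/(0.01 + 0.0347)] × [1 − exp(−0.0447 × 25)] = 15.1%. The 1-KM estimate with censoring at the stop is 1 − exp(−0.25) = 22.1%.

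**6. Missing onset dates.** If 5% of cases (assumed) in an arm with 15% risk have no usable date, an all-treated curve ends at 15% × 0.95 = 14.25%, which is 0.75 points below the table.

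**The case against.** The strongest reply is that this is a naming error. The sentence states its own restriction and pairs the graph with a median time to onset, and 11.1 lists these outputs as times to first TEAE. Read as an onset-time display, the graph is legitimate and so is the median, among patients with the event. That stands, and it is why relabelling is an acceptable remedy for an events-only graph. It does not rescue the text as written, which calls the result cumulative incidence.

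It can also be said that crude risk by arm is tabulated anyway. This is largely right: 11.1 lists tables for TEAEs leading to oral dose reduction and to oral and IV interruption and discontinuation, and anaemia appears through the combined preferred terms. The cover is not complete. No listed table is specific to treatment-related TEAEs leading to dose action, IV delays are counted only under exposure in Section 7.1, and COMBO 11.1 has no rates per 100 patient-treated years such as MONO plans.

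A reader might go further and infer that the graph would reverse the ranking of the arms. Under a model in which Arm A has all of Arm B's events (15%) plus 15 points of added ones, the plotted difference at 6 months is 0.5 × (F_added − 0.875). Added events with a median onset of 4 months (F = 0.655) give −11.0 points, against a true +9.8 (0.15 × 0.655). With a median of 1 month (F = 0.984) they give +5.5 points, against a true +14.8, so there is no reversal. The documents do not show which case applies. The model also fits first-event endpoints imperfectly: an early nivolumab event in a patient who would later have had a rucaparib event replaces that patient's onset time and adds no new case. Reversal is possible but not established.

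**Conclusion.** The display is wrong as specified. The 100% endpoint in every arm with an event, and the loss of any information on risk, follow from the SAP's wording alone. Any size of distortion beyond that endpoint, including the 13.1-point difference that disappears under equal timing, rests on assumed risks and onset times and is illustrative only.

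The consequence is limited to a descriptive safety figure. No hypothesis test uses it, and the main n (%) tables are unaffected. The documents do not support a reading that the plan conceals adverse-event risk by arm. Nor do they establish that the graph extends to immune-mediated events, since 11.2 says only that these are summarised similarly. That should be clarified.

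**What to change.** Amend COMBO SAP 11.1 as follows.

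- **Risk set and estimator.** Draw the curves in all treated patients of the Safety Population, by arm as treated, with an Aalen-Johansen estimate.
- **Competing events for events acting on a study drug.** Death, and permanent discontinuation of that drug for another reason.
- **Competing events for anaemia.** Death, and the end of the treatment-emergent window (28 days after the last oral dose or 152 days after the last IV dose, whichever is later). Naming death alone would leave exit at the end of the window to be handled as censoring, which brings back the inflation in step 5.
- **Missing onset dates.** Footnote by arm the number of events without a usable date. The end of the curve and the n (%) table should then agree apart from these.
- **Events-only output.** Keep the median time to onset, and any events-only graph, only if labelled *time to onset among patients with the event*.
- **Section 11.2.** State whether the display applies to immune-mediated events.

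The cost is a few sentences and a standard procedure, with no new data. Section 7.1 says: "At the time of the visit cut-off, all patients will have discontinued treatment", for protocol-specified reasons or at the 24-month cap, so follow-up for drug-action events will be essentially complete.

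For ATHENA-MONO, whose primary analysis was performed in March 2022 (COMBO SAP 3.5), a relabelled or supplementary figure is enough.
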